## Protocol Synopsis

Title	Islet Transplantation in Type I Diabetes with LEA29Y (belatacept) Maintenance Therapy
Short Title	LEA29Y Emory Edmonton Protocol (LEEP)
Clinical Phase	Phase 2
IND Sponsor	DAIT/NIAID/NIH
IND Number	BB-IND 9336
Activation Date	March 2008
Accrual Objective	10
Accrual Period	24 months
Study Duration	24 months after the final transplant
Study Design	This trial is a prospective, two-center, open-label, pilot study of islet transplantation assessing the safety and efficacy of a steroid-free, calcineurin inhibitor-free based immunosuppressive regimen with belatacept in subjects with long-standing type 1 diabetes (T1D) that is refractory to intensive insulin therapy.
Treatment Description	Subjects will receive up to 3 separate islet transplants to achieve insulin independence. For immunosuppression, the subjects will receive belatacept, basiliximab, and mycophenolate mofetil administered in an open-label fashion.
Primary Endpoint	The proportion of insulin-independent subjects at day 75 ( $\pm$ 5 days) following the first islet transplant.
Secondary Endpoints	
The key secondary endpoint is the proportion of subjects with an HbA1c <math><7.0\%</math> AND free of severe hypoglycemic events from Day 28 to Day 365, inclusive, after the first islet transplant.
 
The other secondary endpoint is the proportion of subjects with an HbA1c <math><7.0\%</math> AND free of severe hypoglycemic events from Day 28 to Day 365, inclusive, after the final islet transplant.
 
Efficacy Endpoints
 
At <math>75 \pm 5</math> days following the first islet transplant and following each subsequent islet transplant(s):
 

• The percent reduction in insulin requirements

• HbA1c

• Mean amplitude of glycemic excursions (MAGE)

• Glycemic lability index (LI)

• Ryan hypoglycemia severity (HYPO) score

- Basal (fasting) and 90-min glucose and c-peptide derived from the mixed-meal tolerance test (MMTT)
- $\beta$ -score
- C-peptide: (glucose  $\times$  creatinine) ratio
- Acute insulin response to glucose ( $AIR_{glu}$ ), insulin sensitivity, and disposition index (DI) derived from the insulin-modified frequently-sampled IV glucose tolerance (FSIGT) test

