Protocol Eligible	Participants will be considered 'protocol eligible' once all screening assessments required to confirm eligibility in the study have been completed.

Primary Nonfunction (PNF)	Graft failure that occurs between 3 and 7 days post-transplant.
Severe Hypoglycemic Event Definition	A severe hypoglycemic event is defined as an event with one of the following symptoms: memory loss; confusion; uncontrollable behavior; irrational behavior; unusual difficulty in awakening; suspected seizure; seizure; loss of consciousness; or visual symptoms, in which the subject was unable to treat him/herself and which was associated with either a blood glucose level < 54 mg/dL (3.0 mmol/L) or prompt recovery after oral carbohydrate, IV glucose, or glucagon administration).
Wait List	Protocol eligible participants who have been listed for islet transplant with UNOS or an equivalent transplant network.
Women of Child Bearing Potential (WOCBP)	WOCBP includes any female who has experienced menarche and who has not undergone successful surgical sterilization (hysterectomy, bilateral tubal ligation, or bilateral oophorectomy) or is not postmenopausal (defined as amenorrhea $\geq$ 12 consecutive months; or women on hormone replacement therapy with documented serum follicle stimulating hormone level > 35 mIU/mL). Even women who are using oral, implanted, or injectable contraceptive hormones or mechanical products such as an intrauterine device or barrier methods (diaphragm, condoms, spermicides) to prevent pregnancy or practicing abstinence or where the partner is sterile (e.g., vasectomy), should be considered to be of child bearing potential.

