No data are available on the compatibility of belatacept with other IV substances. Other drug substances should not be added or infused simultaneously through the same IV line. Assure adequate, appropriate flushing between each drug substance if multiple drugs are administered through the same line sequentially.

Recommended safety measures for preparation and handling include protective clothing, gloves, and safety cabinets.

Subjects will receive NULOJIX® (belatacept) 10mg/kg through a peripheral vein on Day 0 and post-operative days 4, 14, 28, 56, 84. After Day 84 subjects will receive belatacept at a maintenance dose of 5 mg/kg every 4 weeks for the duration of study follow-up (2 years after the final islet transplant). Infusion of the Day 0 dose should be started after the islet product is deemed suitable for transplant and completed prior to beginning the transplant. Infusion doses will be based upon the subject's actual body weight at study Day 0 and will not be modified

during the course of the study unless there is a change in body weight  $\pm 10\%$  of the Day 0 weight. For second or third islet transplants performed after day 85, subjects will remain on the current maintenance dose and schedule of belatacept (5 mg/kg monthly), without modification. In addition to the maintenance doses, subjects will receive a single supplementary dose of belatacept 10 mg/kg. If the second or third transplant is performed within 14 days after the last dose of belatacept, the supplementary dose will be administered approximately 14 days (within the  $\pm 4$  day visit window) after the last dose of belatacept. If the transplant is performed more than 14 days of the last dose of belatacept, the supplementary dose will be administered within 24 hours of the transplant. This supplementary dose was chosen so as to approximate serum trough concentrations that are attained in the first 6-8 weeks after the initial transplant.

NOTE: If the maintenance dose is scheduled to be given within four days of a supplemental dose, the maintenance dose should not be given. Subjects will resume maintenance dosing at their next scheduled visit.

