## **5.2 Immunosuppression Medications**

The immunosuppressive agents used for the initial and subsequent islet transplants will be identical.

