#### 5.7.1.2 GRAFT FAILURE

Subjects who experience graft failure will be maintained on their current immunosuppressive regimen as long as a subsequent transplant is possible. If/when it is determined that a subject will not receive a subsequent transplant, then immunosuppression will be stopped and the subject will move to the reduced follow-up schedule (see section 5.7.2).

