### **6.2.2 Site Suspension and Review**

Study enrollment and initial islet transplants will be suspended (placed on hold) at a participating clinical site, pending expedited review of all pertinent data by the IRB, the NIAID, the NIDDK, and the NIDDK DSMB, if any one of the following occurs:

1. Any grade 5 AE that is possibly, probably, or definitely related to the study treatment regimen (Section 5); or
2. Two SAEs related to the islet transplant procedure (e.g., bleeding, thrombosis, gall bladder injury); or
3. Two consecutive primary non-functioning transplants (see Study Definitions).

After any site is placed on hold, no additional transplants will be performed at that site until the CIT Steering Committee and DSMB meet either in person or by conference call to review in depth the results and circumstances surrounding the islet functional failure or SAE to determine whether the trial enrollment of new subjects and conduct of additional transplants could be safely resumed at that site, or whether there could be implications for the continuation of the entire proposed pilot protocol also at other affiliated sites testing the same protocol.

In all cases of PNF, no further belatacept will be administered and subjects will be asked to temporarily continue on the standard immunosuppression to decrease the risk of sensitization that could increase the risk of poor outcome should future transplants occur. A tapering schedule will be applied until immunosuppressants are completely discontinued.

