### 7.6.1 Second Islet Transplant

Islet transplant recipients with partial islet graft function (see Study Definitions) will be considered for a second islet transplant in the interim between 85 days and 8 months post-initial infusion. Islet transplant recipients with **graft failure** will be considered for a second islet transplant before 85 days post-initial infusion. In addition to meeting the criteria outlined below, approval from the Steering Committee must be obtained in advance. Please refer to the MOP for details on this process, which includes review of the potency testing from the first transplant product and post-transplant clinical data.

In order to be eligible for a **second islet transplant**, the following requirements must be met:

1. Subject received  $\geq 5,000$  IE/kg with the first transplant, but failed to achieve or maintain insulin independence.
2. Subject has been compliant with study monitoring and prescribed immunosuppressive therapy.
3. Subject has no unresolved SAEs.
4. No evidence of progressive renal dysfunction, with blood creatinine rising above 2.0 mg/dL (177  $\mu$ mol/L).
5. No evidence of hypersensitization, allergic responses, or other potentially serious drug reactions to medications required by the protocol.
6. PRA  $\leq 50\%$  by flow cytometry (assessment performed locally) and the alloantibody specificity not cross-reactive with antigen(s) present in the subsequent islet preparation in order to avoid unacceptable antigen(s).
7. Absence of any medical condition that, in the opinion of the investigator, will interfere with a safe and successful second islet transplant.

If graft failure occurs after the second islet transplant, these recipients will be considered **treatment failures** with no islet graft function, and immunosuppression will be withdrawn.

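### For primary non-function, Section 6.2.2 tapers immunosuppression to zero while Section 5.7.1.2 keeps the regimen for a possible second transplant, and no text says whether belatacept resumes

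*Protocol*

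**What the plan says.** - **Definition.** Study Definitions describe PNF as: "Graft failure that occurs between 3 and 7 days post-transplant". Every PNF subject is therefore a graft-failure subject.
- **Graft-failure rule (Section 5.7.1.2).** "Subjects who experience graft failure will be maintained on their current immunosuppressive regimen as long as a subsequent transplant is possible". Immunosuppression stops once it is settled that no further transplant will follow. PNF is not excepted.
- **PNF rule (Section 6.2.2).** "In all cases of PNF, no further belatacept will be administered". Subjects are asked to stay on standard immunosuppression for a time, to limit sensitization in case of a future transplant. Then: "A tapering schedule will be applied until immunosuppressants are completely discontinued".
- **Second transplant (Section 7.6.1).** Recipients with graft failure "will be considered for a second islet transplant before 85 days post-initial infusion", subject to seven listed criteria and advance Steering Committee approval. None of the criteria excludes PNF.
- **Agents at repeat transplants.** Section 5.2 states: "The immunosuppressive agents used for the initial and subsequent islet transplants will be identical". That section lists mycophenolate mofetil (MMF), basiliximab and tacrolimus; belatacept is in Section 5.1.2. The Synopsis does count belatacept as immunosuppression: "For immunosuppression, the subjects will receive belatacept, basiliximab, and mycophenolate mofetil administered in an open-label fashion".
- **Belatacept calendar (Sections 5.1.2.2 and 7.4).** 10 mg/kg on Days 0, 4, 14, 28, 56 and 84, then 5 mg/kg every 4 weeks until two years after the final transplant. The special provision for repeat transplants is limited by date: "For second or third islet transplants performed after day 85, subjects will remain on the current maintenance dose and schedule of belatacept", with one supplementary 10 mg/kg dose.

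**The concern.** A PNF subject who is a candidate for a second transplant falls under both Section 5.7.1.2 and Section 6.2.2, and neither refers to the other. One keeps the regimen because another transplant is possible. The other withdraws belatacept and then removes the remaining drugs without making the taper depend on whether a transplant is still planned. Section 6.2.2 is also a patient-level dosing order placed under site suspension, where a treating physician may not look for it.

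At stake is consistent handling of the investigational drug in a subject about to receive a second graft. The endpoints exposed are those in Section 4.1.2 counted from a subsequent or final transplant, and the safety endpoints on regimen change, discontinuation of immunosuppression and new anti-HLA antibodies. The taper may also bear on eligibility. Section 7.6.1 requires a PRA of at most 50%, and Section 1.5.1.3 reports PRA above 20% in about 25% of recipients on maintenance immunosuppression against about 84% of those who lost function and stopped it. Those figures use a different threshold and are not specific to PNF, so they show direction only.

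**Working it through.** The protocol gives no figure to reproduce here. The check sets the rules side by side and counts doses.

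**Step 1: do both rules apply?** PNF is graft failure at Days 3 to 7, so 5.7.1.2 applies by definition and 6.2.2 applies by name. Section 7.6.1 makes the same subject a candidate for a second transplant before Day 85, which satisfies the condition in 5.7.1.2.

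**Step 2: compare the orders for a PNF subject awaiting a second transplant.**

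| Item | 5.7.1.2 | 6.2.2 |
|---|---|---|
| Belatacept | continue while a transplant is possible | stop |
| Other agents | continue while a transplant is possible | continue temporarily, then taper to zero |
| Trigger for stopping | decision that no transplant will follow | none stated |
| Belatacept at the second transplant | already running | not addressed |

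**Step 3: size of the belatacept difference.** The calendar has 6 doses of 10 mg/kg through Day 84, or 6 × 10 = 60 mg/kg. Assume PNF is established after the Day 4 dose and before Day 14, with no re-transplant by Day 84.
- Under 5.7.1.2: Days 14, 28, 56 and 84, so 4 × 10 = 40 mg/kg.
- Under 6.2.2: 0.
- If PNF is established before the Day 4 dose, 6.2.2 removes 5 doses, or 50 mg/kg.

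For an illustrative re-transplant on Day 45, the last belatacept dose was 45 − 4 = 41 days earlier under 6.2.2 and 45 − 28 = 17 days earlier under 5.7.1.2.

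**Step 4: re-transplants on or before Day 85 (clarification only).** The supplement provision starts after Day 85, while 7.6.1 places graft-failure subjects before Day 85. Outside PNF the stated calendar runs on by default. A re-transplant on Day 45 is then followed by doses on Days 56, 84 and 112 within the next 84 days: 10 + 10 + 5 = 25 mg/kg, or 35 mg/kg if the supplement were extended. On Day 72 it is Days 84, 112 and 140: 10 + 5 + 5 = 20 mg/kg, or 30 mg/kg. The open question is one 10 mg/kg infusion.

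Under the default, a re-transplant on Days 43–54 or 71–82 (12 + 12 = 24 days) falls more than 14 days after the last dose and waits 2 to 13 days for the next (56 − 54 to 56 − 43; 84 − 82 to 84 − 71). After Day 85 the supplement would be due within 24 hours in that position. But the later rule itself accepts a similar wait when the last dose is recent: after a Day 112 dose and a Day 113 transplant, the supplement falls at about Day 126, and 126 − 113 = 13 days. The wait does not demonstrate under-exposure.

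**The case against.** The best defence is that 6.2.2 is the specific rule for a defined subset and overrides the general rule in 5.7.1.2. The protocol also often separates belatacept, the secondary investigational agent in Section 5.1, from the immunosuppression medications in Section 5.2, and 6.2.2 makes the same split. On that reading belatacept stops after PNF, MMF continues while a transplant is possible, and the taper follows. Section 5.7.2 lists graft failure among the permitted reasons to discontinue study treatment, so stopping is not foreign to the protocol.

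Much of this stands. It settles the belatacept stop, and the 40 mg/kg difference then reflects a missing cross-reference rather than a true choice. It does not settle the taper: 6.2.2 attaches no condition to it, so tying it to the transplant decision means importing the condition from 5.7.1.2. It also leaves the second transplant open. Section 6.2.2 foresees that transplant but names no point at which belatacept resumes, and the sentence in 5.2 on identical agents is weak support either way because that section does not list belatacept.

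A reader might infer more about early re-transplants in general: that the days before Day 85 have no belatacept rule, or that the course restarts and delivers 60 mg/kg over the following 84 days. The documents do not support either. Sections 5.1.2.2 and 7.4 run one calendar to the end of follow-up and nothing suspends it. The restart idea rests on the time-axis headings of Figure 2 and Appendix 3, which order no dosing. Limiting the supplement to the 5 mg/kg phase is also coherent with its stated aim of matching early trough levels.

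Steering Committee approval is a central control on every second transplant, and the Manual of Procedures, which is not shown, may guide single cases.

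**Conclusion.** The point holds for PNF. Sections 5.7.1.2 and 6.2.2 conflict as written; even with 6.2.2 governing belatacept, its unconditional taper contradicts 5.7.1.2, and no text says whether belatacept returns at a second transplant. For re-transplants on or before Day 85 in general, continuation of the calendar is the default and only a confirming sentence is needed.

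Severity is minor. The trial has 10 subjects, and the problem needs PNF, continued eligibility, committee approval and a new compatible preparation. The dose counts assume the Day 4 dose was given and no re-transplant came sooner; Day 45 is an illustration.

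An effect on the primary endpoint should not be inferred. Graft failure means C-peptide below 0.3 ng/mL, whereas insulin independence needs at least 0.5 ng/mL, and a footnote to Appendix 1 uses the tests at graft failure for the Day 75 calculations. Nor is an exposure deficit shown. What is affected is treatment consistency and the endpoints counted from subsequent and final transplants.

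**What to change.** 1. **Section 5.7.1.2:** add an exception for primary non-function that points to 6.2.2.
2. **Section 6.2.2:** start the taper only once it is determined that no second transplant will occur, and state that belatacept resumes at Day 0 of an approved second transplant, naming dose and schedule. Alternatively, state in Section 7.6.1 that PNF subjects are not eligible for a second transplant.
3. **Sections 5.1.2.2 and 7.4 (clarification):** add one sentence for repeat transplants on or before Day 85, either confirming that the existing calendar continues or extending the supplementary dose to them.

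The choice of dose is the sponsor's. The cost is a short protocol amendment with no added patients. Extending the supplement adds one infusion per early re-transplant; confirming the calendar adds none. Resuming belatacept after PNF adds the infusions of whichever schedule the sponsor names, in those subjects only.

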## 7. STUDY PROCEDURES

### 7.1 Enrollment and Screening

Patients who meet the general inclusion criteria for this study will be approached regarding their participation. The study procedures, risks, and potential benefits will be discussed with the potential study subject in lay language. The potential study subject will have an opportunity to review the informed consent and ask questions.

Once informed consent has been obtained, the subject will be enrolled and assigned a unique subject identification number. Subject eligibility will be confirmed through the performance of the screening visit procedures detailed in the Schedule of Events (Appendix 1). More than one visit may be necessary to complete all of the screening procedures. Patients who enroll in this trial may have had some of the required screening tests done prior to signing the enrollment consent document as part of their routine diabetes care or a previous assessment for standard islet and/or pancreas transplantation at the participating sites. Results from assessments completed prior to signing informed consent, must be current within the windows stated in the table below.

*Table 2: Time frames for screening assessments*

Screening Assessments	Allowable timeframe prior to the date of consent
EBV IgG	No limit. Positive result required for eligibility
Retinopathy evaluation; Physical exam; CXR; Abdominal US; ECG; Cardiac Stress Test or Angiogram; PPD; TSH; Serology; Coagulation;	Within one year
CBC; Chemistry; Lipids; Mammogram	Within 6 months

The screening pregnancy test, first morning spot urine, and blood draws for all central laboratory assessments must be done at the study site after informed consent has been signed. Pregnancy and blood transfusion history will be collected and provided to the central lab for PRA analysis.

In addition to the protocol required screening assessments, subjects should meet site-specific requirements for transplant.

### 7.2 Waiting List / Baseline

After completion of the screening assessments required to confirm eligibility for the study, he/she will be listed for an islet transplant. During this period when subjects are awaiting their first transplant, the remaining screening assessments - FSIGT, CGMS, and retinal photos - should be completed as time allows. If retinal photos cannot be obtained at WL/BL, they should not be collected post-randomization. Waitlist assessments will be repeated at pre-defined intervals as detailed in Appendix 1. Results from assessments done closest to the start of immunosuppression will be used as the subject's baseline values. All one-time waitlist/baseline assessments should be completed on Day -2, whenever possible, but always

prior to the start of immunosuppression. As in any other transplant situation, medical conditions that arise (*e.g.*, new serious infection, malignancy, compliance issues, etc.) will automatically trigger a re-evaluation to determine if the subject remains qualified for the protocol. Only qualified subjects may proceed to donor organ matching and transplant.

### **7.3 Randomization, Islet Transplant, and Study Treatment**

Once a compatible islet prep becomes available, subject eligibility will be re-confirmed. Eligible subjects will be randomized on Day -2 relative to transplant, between this Phase 2 trial and the multi-center Phase 3 trial. Randomizations will occur at a ratio of 2:1, where 2 participants are assigned to CIT07 for every subject assigned to the site-specific Phase 2 trial. Subjects randomized to this Phase 2 trial will receive their initial study drug infusion of belatacept 10mg/kg by peripheral IV over 30 minutes, followed by the islet transplant. The infusion of islets must be initiated within 24 hours of completion of the belatacept infusion.

### **7.4 Post-transplant Study Treatment Visits**

Subjects will receive NULOJIX® (belatacept) 10mg/kg by peripheral IV over 30 minutes on post-operative days 4, 14, 28, 56, 84. After Day 84 subjects will receive belatacept at a maintenance dose of 5mg/kg every 4 weeks for the duration of study follow-up (24 months after the final transplant). Infusion doses will be based upon the subject's actual body weight at study Day 0 and will not be modified during the course of the study unless there is a change in body weight  $\pm 10\%$  of the Day 0 weight. For second or third islet transplants performed after day 85, subjects will remain on the current maintenance dose and schedule of belatacept (5 mg/kg monthly), without modification. In addition to the maintenance doses, subjects will receive a single supplementary dose of belatacept 10 mg/kg. If the second or third transplant is performed within 14 days of the last dose of belatacept, the supplementary dose will be administered approximately 14 days (within the  $\pm 4$  day visit window) after the last dose of belatacept. If the transplant is performed more than 14 days of the last dose of belatacept, the supplementary dose will be administered within 24 hours of the transplant. This supplementary dose was chosen so as to approximate serum trough concentrations that are attained in the first 6-8 weeks after the initial transplant.

NOTE: If the maintenance dose is scheduled to be given within four days of a supplemental dose, the maintenance dose should not be given. Subjects will resume maintenance dosing at their next scheduled visit.

